9. STATISTICAL CONSIDERATIONS

9.1 General Design Issues_

The R61 phase of this clinical trial - Effects of Music Based Intervention (MBI) on Pain Response and Neurodevelopment in Preterm Infants – is exploratory and designed to inform planning of the R33 phase.

Primary Objective (1): Characterize differences in preterm pain responses between MBI and controls. Premature infant pain profiles (PIPP) include physiologic, behavioral, and contextual measures which identifies differences in pain responses between MBI and controls while still in the neonatal intensive care unit (NICU). Central EEG amplitude changes have been timelocked with painful procedures in term infants. We will explore if PIPP scores and central EEG amplitudes change with MBI compared to controls.

This primary objective(1) addresses the first hypothesis and the milestone measures (3 and 4) described in Appendix A.

• Hypothesis 1: MBI will show improved pain responses, with lower PIPP scores and attenuated central EEG amplitude changes during painful procedures, in comparison to the control cohort.

Measure 3) PIPP scores comparing MBI to controls during a painful procedure.

Measure 4) Central EEG amplitude changes comparing MBI to controls during a painful procedure.

Primary Objective (2): Identify differences between MBI and controls in preterm brain maturation and early neurodevelopment.

EEG is a surrogate marker for real time brain function during sleep-wake cycles. Because preterm brain networks develop during sleep, sleep duration is a strong indicator of brain maturation. Serial biweekly EEGs of preterm infants can quantify sleep duration trends and track MBI's influence on sleep.

Due to the natural limitations of evaluating immature neonatal nervous systems, ERPs have been utilized to study early neurodevelopment. ERPs quantify electrical brain potentials changes time-locked with a stimulus.

Auditory ERPs performed at 43-48 weeks corrected age evaluates attention and discrimination between familiar and novel stimuli - early neurodevelopmental signs of recognition memory function and perceptual learning.

This primary objective(2) addresses the below two hypotheses and the milestone measures (1 and 2) described in Appendix A.

• Hypothesis 2: MBI will enhance preterm EEG brain maturation in comparison to controls.

Measure 1) Average sleep (REM + non-REM) duration difference between MBI and controls using EEG.

• Hypothesis 3: ERPs at 1 month (43-48 weeks) corrected age will show that MBI has a greater impact on early neurodevelopment when compared to controls.

Measure 2) Late Slow Wave amplitude difference in auditory ERPs comparing MBI to controls.

9.2 Sample Size and Randomization

The R61 phase is exploratory. Based on the number of eligible infants and assuming 60% of eligible subjects enrollment, we can feasibly enroll 60 infants in 1.5 years.. This sample size is similar to or larger than other MBI studies in infants.^{21,23,68,107}

The clinical measure Premature Infant Pain Profile (PIPP) at 4 weeks is the primary outcome for the R61-phase pilot clinical trial. With expected recruitment of at least 60 preterms, expected 50 completed PIPPs at 4 weeks represents a loss to follow-up of $(60-50)/60 = \sim 17\%$. Such a loss rate is slightly more conservative than previous studies completed in the University of Minnesota NICU (which has had ~15% loss rates). This sample size is similar to or larger than other previous MBI studies in infants.

With 50 completed PIPPs at 4 weeks, for comparing MBI to control (25 per group), there is 80% power to detect a group difference in PIPP of 2.9 and 85% power to detect a group difference in PIPP of 3.1. These calculations assume a between-infant standard deviation of 3.6, estimated from the placebo group of a recent study of sucrose as an analgesic for pain from a standard-of-care heel lance. These calculations were carried out in SAS with the following code:

proc power;

twosamplemeans test=diff meandiff = . stddev = **3.6** npergroup = **25**

```
power = 0.80 0.85
    alpha = 0.05
run;
```

;

The R61 exploratory phase data from primary outcome clinical measure PIPP at 4 weeks will be utilized to assist in planning of the R33 phase. The associations of baseline characteristics (infant, e.g. birthweight, and maternal pregnancy history, etc) may inform the design of the R33 phase. For example, these secondary analyses might indicate that we should stratify randomization in the R33 phase by a dichotomized infant birthweight. These analyses, using linear models or non-parametric alternatives if needed (e.g., measures are highly skewed), will use both intervention groups and we will examine the magnitudes of associations in each group and, if appropriate, in the pooled groups.

Treatment Assignment Procedures

Once eligibility has been confirmed and consent obtained. Randomization will be accomplished through the use of randomization tables, stratified by sex and within each stratum use randomly allocated block sizes of 2 and 4. These will be prepared by the study statistician ([name]).

Blinding will be maintained by using identical headphones and MP3 players for all subjects. The PI, any personnel involved in collecting the clinical outcomes (e.g., PIPP) or collecting or quantifying EEG outcomes, and the statistician will be blinded. The statistician will be aware of blinded treatment group, so that e.g. safety summaries by blinded treatment group can be prepared for the Data Safety and Monitoring Board (DSMB) closed sessions if it so requests. Should the DSMB request unblinded comparisons, the study team will contract with the University of Minnesota CTSI's Biostatistical Design and Analysis Center (BDAC) for an independent statistician to work with the DSMB using unblinded data.

The unblinded staff includes [name] (music therapist) and [name] (Director of the NICU). [name] will prepare the music players. Both will be unblinded to handle randomization, delivery of interventions, and preparations of unblinded reports to the independent study monitors. They will not be involved with data monitoring, analyses, or outcome assessments.

The study coordinators who are assessing the PIPP will wear earplugs and noise cancelling headphones, which will ensure that s/he cannot hear what is emanating from the infant's headphones. In addition, family members and NICU staff will be reminded frequently to not disclose what they think they hear coming from the infant's headphones.

9.3 Definition of Populations

N/A

9.4 Interim Analyses and Stopping Rules

N/A

9.5 Outcomes: Milestone Measures and Data Analyses

Measure 1: Average sleep (REM+nonREM) duration difference between MBI and controls using EEG. Normal preterm brain development is dependent on cycling between wakefulness and sleep with sleep durations gradually increasing by about 5% increments every two weeks until term age. EEG will be used to measure the average duration of sleep (REM + non-REM) between MBI and controls. Average sleep duration measurements will determine if MBI promotes/enhances brain maturation.

Statistical Analysis: Four quality sleep durations from within each EEG session will be averaged per-infant per-timepoint (one EEG session for each of the 4 age timepoints, 30 weeks, 32 weeks, 34 weeks, 36 weeks). At each timepoint, average sleep duration will be compared between MBI infants and controls. Milestone threshold will be reached if >5% longer average durations of sleep are found in the MBI cohort compared to controls in any 1 or more of the serial EEGs.

Measure 2: Late Slow Wave amplitude difference in auditory ERPs comparing MBI to controls. Due to immature nervous systems, early infant neurodevelopment studies have centered on attentional capture paradigms using ERPs. ERPs quantify changes in electrical brain potentials time-locked to a stimulus and are widely used to study cognitive abilities such as learning, discrimination, attention, and memory. At one month age, the ERP Late Slow Wave of a mom/stranger stimulus is considered a reflection of perceptual learning and memory. ERP Late Slow amplitude measurements will determine if MBI enhances neurodevelopment.

Statistical Analysis: ERP Late Slow Wave amplitudes from the 100 trials of the auditory recognition task will be averaged. Within-infant average Late Slow Wave amplitudes across mother's voice trials minus the same average across stranger's voice trials will be computed and averaged. Mother-vs-stranger Late Slow Wave average difference between MBI and controls will be compared. Milestone threshold will be reached if $\ge 1 \ \mu V$ greater amplitude difference in ERPs of the MBI cohort compared to controls is found at one month adjusted age.

Measure 3: PIPP scores comparing MBI to controls during a painful procedure. The premature infant pain profile (PIPP) is well established and has undergone extensive psychometric testing. Music creates a sense of familiarity and security in preterm infants and redirects their attention away from the painful stimulus; thus, PIPP scores will be used to measure if MBI has an effect on pain response in comparison to controls.

Statistical Analysis: The PIPP will be scored at 3 age timepoints (30 weeks, 32 weeks, 34 weeks). At each timepoint, average PIPP among MBI infants will be compared to average PIPP among control infants. Milestone threshold will be reached if MBI cohort PIPP scores are \geq 1 point lower than controls at any 1 or more of the scoring points.

Measure 4: Central EEG amplitude changes comparing MBI to controls during a painful procedure. The heel lance painful procedure has been shown to evoke central EEG activity with significantly higher amplitudes, $\ge 10 \ \mu\text{V}$ in infants. EEG will be used to measure amplitude changes in central EEG activity to determine if MBI alters responses to a painful procedure.

Statistical Analysis: Three quantifiable changes in central EEG amplitudes will be collected - one for each age timepoint at which a heel lance is done (at 30, 32, and 34 weeks). Within-infant central EEG amplitude differences between heel sticks and resting states will be computed. Average central EEG amplitude change (heel-stick minus resting-state) among MBI infants will be compared to controls. Milestone threshold is reached if $\geq 10 \ \mu V$ attenuation in central EEG amplitudes occurs with a painful procedure in the MBI cohort compared to controls in any of the serial EEGs.

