1.2 Primary Objective (2)

Aim 2(R61): Identify differences between MBI and controls in preterm brain maturation and early neurodevelopment.

EEG is a surrogate marker for real time brain function during sleep-wake cycles. Because preterm brain networks develop during sleep, sleep duration is a strong indicator of brain maturation. Serial biweekly EEGs of preterm infants can quantify sleep duration trends and track MBI's influence on sleep. To enhance objectivity, innovative EEG machine-learning tools will be applied to the analyses.

• Hypothesis 2: MBI will enhance preterm EEG brain maturation in comparison to controls.

Due to the natural limitations of evaluating immature neonatal nervous systems, ERPs have been utilized to study early neurodevelopment. ERPs quantify electrical brain potentials changes time-locked with a stimulus. Auditory ERPs performed at 1 month (43-48 weeks) corrected age evaluates attention and discrimination between familiar and novel stimuli - early neurodevelopmental signs of recognition memory function and perceptual learning.

• Hypothesis 3: ERPs at 1 month (43-48 weeks) corrected age will show that MBI has a greater impact on early neurodevelopment when compared to controls.

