MBI subjects will receive a total of 1.5 hours of music intervention averaged at 4-5 sessions per week (Figure 2). Music will be alternating: 30 minutes on and 30 minutes off and will be played when the subject is awake to cue pacification and initiate the sleep process. Voice unaccompanied or with single accompanying softly arpeggiated instrument⁶⁶ is best for infants. Lullabies meet these criteria and promote language development due to an emphasis on vowels, rising and falling melodic phrases, and the recognition of soothing sounds. Lullabies will all have consistent tempos, with the melody in higher range sung by female or children as infants hear these pitches best.66 As it is recommended to change song order to increase stimulation, habituation, and neurological development, we will use ten playlists. MP3 players will be loaded in advance with the entire 6 weeks

of music. Within each week, order of the playlists will be randomly assigned and prepared in advance by [name]. MBI will have minimal interference with routine medical care. Study coordinators will monitor for any distress from music: finger splay, grimace, vital sign disturbance, or persistent crying.⁶⁷ If crying lasts longer than 5 minutes, the intervention will be stopped for that day's session. Blinding will be maintained by using identical headphones and MP3 players for all subjects. Headphones will be placed on each side of infant's head such that sound stimuli are received binaurally.⁶⁶ Music amplitude will be no more than 70 dB on Scale C.^{15,66,68}

Daily electronic volume level checks will avoid the need for listening checks of the headphones. Headphones will be placed 1 cm away from the ears to avoid discomfort from headphone compression. The headphones will either play music or silence for the control group.

Figure 4: Every two weeks, 30 hour EEG* recordings will capture two sessions of background frequencies and changes that occur with Session 1) MBI or Control intervention or Session 2) [MBI + pain] or [Control + pain]

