9.6 Missing Data

With regards to missing data, the built-in loss rate of 17% includes loss of subjects and also loss due to missing data. Thus, with our recruitment of 60 subjects, we should still be able to reach our 50 subject target completing PIPP data at 4 weeks of MBI.

This pilot clinical trial in the R61 phase is sufficiently small in sample size that imputation methods (e.g., missing week 4 PIPP value or sleep duration) are likely to perform poorly, specifically are likely to add substantial noise to the quantification of the Go/NoGo outcomes. The Go/NoGo quantifications will be computed without imputation and compared to the declared thresholds. Detailed infant and maternal characteristics from baseline assessments will be able to well describe the characteristics of those infants with missing data compared to those with complete data.

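### Measure 1 averages only four sleep periods from an EEG described as 30 hours, with no rule for choosing them; averaging all scorable periods would cut avoidable noise in the >5% milestone.

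*Combined protocol and SAP*

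**What the plan says.** Section 9.5 of the combined protocol and SAP defines the analysed value for Measure 1: "Four quality sleep durations from within each EEG session will be averaged per-infant per-timepoint". It counts "one EEG session for each of the 4 age timepoints, 30 weeks, 32 weeks, 34 weeks, 36 weeks". The milestone is met if ">5% longer average durations of sleep are found in the MBI cohort compared to controls in any 1 or more of the serial EEGs". The stated background is normal maturation, with "sleep durations gradually increasing by about 5% increments every two weeks until term age".

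The Figure 4 caption in section 3 describes the recordings: "Every two weeks, 30 hour EEG* recordings will capture two sessions of background frequencies". One of the two sessions includes the painful procedure.

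Section 9.6 states how the decision is taken: "The Go/NoGo quantifications will be computed without imputation and compared to the declared thresholds". No test or interval is attached to the Measure 1 comparison.

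Two safeguards are relevant. Section 1.2, in the paragraph leading to Hypothesis 2, says "To enhance objectivity, innovative EEG machine-learning tools will be applied to the analyses". Sections 6.2.3 and 9.2 blind the personnel who collect or quantify EEG outcomes.

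The documents do not say what makes a sleep period a *quality* one, where a period starts and ends, which four are used if more than four qualify, what happens if fewer do, or which part of the recording they come from.

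**The concern.** An infant's value at each timepoint rests on four periods, although the recording probably holds many more. This has two consequences.

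First, a mean of four periods carries more within-infant variation than a mean of all usable periods. The extra error is avoidable, because the EEG has been recorded anyway.

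Second, with no selection rule, two competent scorers or two algorithms could take different fours from the same recording and get different values. That makes the result harder to reproduce and adds further noise.

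Both feed straight into a Go/NoGo decision. The threshold is >5%, about the size of one two-week maturation step by the plan's own account, and the estimate is compared with it with no allowance for its error. The revision history (version 2.0b) says the Go/NoGo criteria were designed with equal weight, so a noisy Measure 1 affects the decision on the R33 phase.

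**Working it through.** **The plan's own figures.** There is no SD, power or precision figure for Measure 1. The only power calculation (section 9.2) is for PIPP at 4 weeks: SD 3.6, 25 per group, alpha 0.05. It reproduces with a two-sided two-sample t-test, giving detectable differences of 2.91 at 80% power and 3.11 at 85%, against the stated 2.9 and 3.1. It has no bearing on sleep duration.

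**Inputs for Measure 1**
- Periods used: k = 4 (section 9.5).
- Threshold: 5%, read as a relative difference (section 9.5).
- Infants per arm: n = 25. Assumed; borrowed from the PIPP completer figure in section 9.2.
- Between-infant CV (CVb): 10-20%. Assumed.
- Period-to-period CV within an infant (CVw): 30-70%. Assumed.
- Scorable periods in the recording: 20. Assumed.

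**Formulas.** Treat periods as independent draws within an infant.
- Variance of an infant's mean, relative scale: V(k) = CVb² + CVw²/k
- Standard error of the relative arm difference: SE(k) = √(2·V(k)/n)
- Chance of exceeding 5% at one visit with no true effect: 1 − Φ(5/SE), with SE in percent
- Variance ratio: V(4)/V(20)

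**Central case, CVb = 0.15 and CVw = 0.5**
- V(4) = 0.0225 + 0.25/4 = 0.0850; SE = √(2 × 0.0850/25) = 8.2%
- V(20) = 0.0225 + 0.25/20 = 0.0350; SE = √(2 × 0.0350/25) = 5.3%
- Variance ratio = 0.0850/0.0350 = 2.43
- Chance of >5% under no effect: 27% with four, 17% with 20

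**Corners of the assumed range**

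| CVb | CVw | SE, 4 periods | SE, 20 periods | Variance ratio | P(>5%), 4 | P(>5%), 20 |
|---|---|---|---|---|---|---|
| 0.10 | 0.30 | 5.1% | 3.4% | 2.2 | 16% | 7% |
| 0.10 | 0.70 | 10.3% | 5.3% | 3.8 | 31% | 17% |
| 0.20 | 0.30 | 7.1% | 6.0% | 1.4 | 24% | 20% |
| 0.20 | 0.70 | 11.4% | 7.2% | 2.5 | 33% | 24% |

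With four periods the standard error is above 5% at every corner. With 20 it is below 5% only at the first. The gain is smallest where infants differ a lot and periods differ little.

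**Share of sleep used.** In 1,800 minutes, the number of periods is 1,800 × fraction asleep ÷ mean period length. With 50-90% of the time asleep (assumed), four periods cover 5-9% of the sleep if periods average 20 minutes, 15-27% at 60 minutes and 30-53% at 120 minutes. They reach half only if the mean period is at least 112 minutes (50% asleep) to 202 minutes (90% asleep).

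**The case against.** **The tools may already cover this.** The machine-learning sentence in section 1.2 directly follows the text on sleep-duration trends, and section 9.1 gives Hypothesis 2 only one measure, Measure 1. The natural reading is that the tools are meant for this analysis. A reader might infer that the periods are picked by hand and the tools left unused; the documents do not say so. What stands is that no algorithm or selection rule is stated.

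**Blinding.** EEG quantifiers are blinded, so free choice mainly adds noise. A reader might infer bias between arms, but nothing in the documents shows it. In simulated periods (10-30 per recording, CV 30-50%), the four longest average 27-92% above the mean of all periods. That shift applies to both arms under a common rule and largely cancels in a relative comparison, so it should not be set against 5%.

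**Long periods favoured.** One might suppose that *quality* means long and undisturbed. It may equally mean technically scorable. The text does not settle this.

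**The size is assumed.** Every variance input is an assumption, and independence of periods is a simplification. This is correct, and is why a range is shown. The 30-hour figure also carries an asterisk whose note is not visible here, so the claim that most recorded sleep is discarded is an inference, though it holds over nearly all of the assumed range.

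**The larger weakness is elsewhere.** Comparing a point estimate with 5% at any one of four EEGs is the main source of unreliability. The revision history defends that rule as a deliberate exploratory choice and acknowledges inadequate power for hypotheses 1 and 2. This also stands: using all periods leaves that rule untouched.

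**Conclusion.** The point holds as a precision improvement together with a missing selection rule. Section 9.5 fixes the number of periods at four, and no section says how they are chosen. Under the stated assumptions, using all 20 periods lowers the standard error of the arm difference from 5.1-11.4% to 3.4-7.2%, a variance ratio of 1.4 to 3.8. The chance of a false milestone at one visit falls from 16-33% to 7-24%.

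The central variance ratio of 2.43 might be read as a firm gain equal to 2.4 times the sample size; it is one point in that range. A reader might also infer that the change makes the milestone dependable. It does not: in the central case the standard error is still 5.3% after the change.

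The change is worth making because it draws on data already collected for a measure that feeds the R33 decision.

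**What to change.** In section 9.5, Measure 1:

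1. Keep average sleep-period duration (REM + non-REM) as the milestone quantity, and state that >5% is a relative difference.
2. Replace the four-period average with the mean of all periods that meet pre-specified scorability (artifact) criteria. Define the start and end of a period.
3. State which part of the recording is used, the same for both arms. The recording contains a session with the painful procedure, so the plan must say whether that part is in or out.
4. Name the already blinded quantifiers and the machine-learning tools of section 1.2 as the means of scoring.
5. If only four periods can be scored, take them by a fixed rule, such as the first four scorable periods after a set time. Say what happens when fewer than four qualify.
6. Percent of recording time asleep may be reported as supportive. It is a different quantity from period length and should not decide the milestone or inherit its threshold.

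The cost is SAP wording and more scoring or computing time on EEGs already recorded. No new data are needed.

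### Section 9.5 compares raw arm averages and leaves out sex and birth gestational age; adjusting for both is a nearly free option whose effect on precision is probably small

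*Combined protocol and SAP*

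**What the plan says.** Section 9.5 defines the PIPP comparison (Measure 3) as follows: "At each timepoint, average PIPP among MBI infants will be compared to average PIPP among control infants". For sleep (Measure 1) it says: "At each timepoint, average sleep duration will be compared between MBI infants and controls". Measures 2 and 4 are within-infant contrasts that are then averaged and compared by arm. No covariate, stratum term, model or confidence interval appears for any of the four.

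Section 9.6 says how the results are used: "The Go/NoGo quantifications will be computed without imputation and compared to the declared thresholds".

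Two baseline variables are available for every infant. Sex is the randomisation stratum; section 9.2 describes the tables as "stratified by sex and within each stratum use randomly allocated block sizes of 2 and 4". Gestational age at birth is determined at screening (section 6.2.1) and may vary by 14 days either side of 30 weeks. Section 6.2.4 lists gestational age among the seven PIPP items, each scored 0 to 3. Section 9.5 describes "sleep durations gradually increasing by about 5% increments every two weeks until term age". The only linear models in the plan, in section 9.2, examine associations of baseline characteristics with the outcome to help plan the R33 phase. They do not adjust the arm difference.

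The timing labels differ between sections. Section 9.5 refers to "one EEG session for each of the 4 age timepoints, 30 weeks, 32 weeks, 34 weeks, 36 weeks". Section 9.2 says "The clinical measure Premature Infant Pain Profile (PIPP) at 4 weeks is the primary outcome", section 9.6 speaks of the "50 subject target completing PIPP data at 4 weeks of MBI", and the schedule in section 6 runs by study visit.

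**The concern.** The milestone decisions rest on point estimates set directly against thresholds, so sampling noise in an estimate passes into the Go/NoGo result. Where a baseline variable predicts the outcome, including it in the model removes part of that noise without new data. The documents themselves link gestational age to two of the four measures, and sex was judged important enough to stratify on. Leaving both out forgoes whatever precision they offer. At stake is a somewhat less noisy estimate; the validity of the comparison is not in question.

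**Working it through.** **Inputs.** Section 9.2: 25 infants per arm, SD 3.6, alpha 0.05 (taken as two-sided, which reproduces the stated figures). Section 6.2.1: birth ages 28 to 32 weeks, assumed uniform. Section 9.5: PIPP threshold 1 point, sleep threshold 5%, sleep rising about 5% per two weeks. Not in the documents: the share of outcome variance (R²) explained by sex and birth gestational age. A range of 0 to 0.10 is assumed.

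**1. The plan's own figure.** SE = 3.6 × √(2/25) = 1.018. The noncentral t with 48 df gives a detectable difference of 2.911 at 80% power and 3.114 at 85%. The stated 2.9 and 3.1 reproduce.

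**2. Adjusted PIPP estimate.** The SE becomes 1.018 × √(1 − R²), with 46 df. Chance covariate imbalance multiplies the expected variance by (n − 3)/(n − 3 − p), with n = 50: 47/46 for one covariate, 47/45 for two. Stratified blocks already nearly balance sex, so the true cost lies nearer the one-covariate figure. Each range below runs from no imbalance cost to the full two-covariate cost.

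| R² | Detectable at 80% | Power at 2.9 points | Chance of a difference of at least 1 point favouring MBI at one visit, no true effect |
|---|---|---|---|
| unadjusted | 2.91 | 79.7% | 16.3% |
| 0 | 2.91–2.98 | 77.9–79.6% | 16.3–16.8% |
| 0.02 | 2.88–2.95 | 78.7–80.4% | 16.1–16.6% |
| 0.05 | 2.84–2.90 | 79.9–81.6% | 15.7–16.2% |
| 0.10 | 2.76–2.83 | 82.0–83.6% | 15.0–15.6% |

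Break-even R² is 1 − 46/47 = 2.1% to 1 − 45/47 = 4.3%. If R² is zero, the SE rises by √(47/46) − 1 = 1.1% to √(47/45) − 1 = 2.2%.

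**3. What R² might be.** Suppose the gestational-age item is the only link and takes k equally wide levels across the enrolled infants. Then R² = [(k² − 1)/12] × (1 − 1/k²) / 3.6². For k = 2, 3 and 4 this is 1.4%, 4.6% and 9.0%. A sex difference of 0.5 or 1.0 points adds d²/4/3.6² = 0.5% or 1.9%. These values fall on both sides of break-even.

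**4. Simulation.** With sex-stratified blocks of 2 and 4, 60 infants randomised and 50 analysed, the SD of the estimate (unadjusted, then adjusted) was 1.006 and 1.020 at R² 0; 1.037 and 1.033 at 0.03; 1.006 and 0.990 at 0.08; 1.004 and 0.957 at 0.12. The type I error of the adjusted test was 4.7 to 5.6%.

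**5. Sleep.** The SD of birth age is 4/√12 = 1.155 weeks. The chance difference between arms has an SE of 1.155 × √(2/25) = 0.33 weeks. At 2.5% per week that is 0.8% of sleep duration, with a 95% range of about ±1.6%. If the sleep SD is 10 to 20% (assumed), adjusting for age lowers the SE by about 3% to 0%, net of the one-covariate cost.

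**6. Week labels.** An infant born at 32 weeks cannot be assessed at 30 weeks, so the labels in 9.5 work only as nominal names for study visits, which is how sections 6, 9.2 and 9.6 already read.

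**The case against.** The case against is substantial. The trial is an exploratory pilot, nothing in 9.5 is wrong, and choosing a covariate model is partly preference. The documents give no R², and the plausible range includes a small loss. On the decision scale the effect is close to nil: the single-visit chance of crossing the PIPP threshold with no true effect moves from 16.3% to somewhere between 15.0% and 16.8%. The sleep trend in 9.5 concerns age when measured, whereas the covariate is age at birth. The two move together only if infants enrol at similar postnatal ages. The SD of 3.6 comes from another study and may not fit this age mix. All of this stands; it limits the size of the point but does not remove it, because the change costs almost nothing.

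A reader might infer that Visit 1, labelled baseline in section 6, is a pre-intervention measurement that could serve as a strong covariate or should not count as a milestone occasion. The documents do not support building on that. The Figure 4 caption in section 3 describes recordings every two weeks during intervention, and section 6.2.3 has PIPP assessors wear ear protection against sound from the infant's headphones. Neither names Visit 1, but both suggest that outcomes are measured while the device runs. The rule that any one timepoint suffices was chosen deliberately, as the revision history explains, and covariate adjustment neither repairs nor challenges it.

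**Conclusion.** The omission is real and minor. Section 9.5 uses neither the stratum nor birth gestational age when estimating arm differences. For R² between 0 and 0.10 the detectable PIPP difference would move from 2.91 to between about 2.98 and 2.76. That range rests on an assumed R², the plan's SD of 3.6 and 25 infants per arm. Less is at stake for Measures 2 and 4.

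Three stronger readings do not hold. The raw comparison is not biased: randomisation protects it, and ignoring a prognostic stratum only makes its SE somewhat conservative. The sample size is not wrong: the stated figures reproduce. Chance age imbalance could not by itself produce a false sleep milestone, since about ±1.6% is well short of 5%. The differing time labels are a clerical matter and do not affect the estimate.

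**What to change.** Before unblinding, add a short paragraph to section 9.5:

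- The arm difference at each study visit is estimated from a linear model containing arm, sex and birth gestational age, and reported with a 95% confidence interval.
- The adjusted difference is compared with the existing milestone thresholds. For sleep it is expressed as a percentage of the adjusted control mean.
- The unadjusted difference is kept as a sensitivity analysis.
- The 30, 32, 34 and 36 week labels are nominal names for study visits, consistent with sections 6, 9.2 and 9.6.

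The cost is one paragraph, slightly more analysis and two degrees of freedom. Both covariates are already collected and no threshold changes. If neither predicts the outcome, the SE rises by about 1 to 2%.
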